Within each of the 5 study sites, we will randomize 25 (one-week blocks) to the PROCOVAXED intervention and 25 (one-week blocks) to usual care using one-week periods with blocks of concealed size to ensure equal allocation to the two intervention settings. Our randomizations will be computer-based pseudo-random sequences of 7 days periods, stratified by study center. We will develop 60 random sequences separately for each center which will be enough to last the study for up to 14 months. We will stratify sequences by study week period so that 3 centers will be in the control condition for one week and 2 centers will be in the experimental condition for one week, or vice versa. This will minimize the effect of secular trends on the comparison of the intervention. We will generate a 60-week study calendar based on this randomization scheme. To try to maintain masking of allocation, sites will not be notified of their treatment assignment for the next week no more than 3 days prior to that week.

- **Site Orientation and Training**

The Core UCSF Site will develop orientation materials to familiarize the ED Sites with the study protocol. Each site will employ one or more Clinical Research Coordinators (CRCs), who will report to the Site PI and be responsible for day-to-day study implementation. We will develop and disseminate a manual of operating procedures (MOP) with standard personnel training methods, including education kits with scripts, summary cards, and PowerPoint presentations to assist coordinators in the orientation of site clinicians and other staff to our study protocol. We will convene ZOOM conference calls to review this summary and develop plans for optimization of PROCOVAXED platforms to improve usability and workflow. We will refine procedures with updates delivered to the site PIs during weekly ZOOM conferences.

- **Study Hotline and Quality Assurance**

We will maintain a study hotline and encourage study personnel to contact the PI and Central Study Coordinator for all issues and queries. Hotline hours will be during primary study hours (weekday 8 a.m. to 5 p.m. PST).

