PROCOVAXED Trial Workflow on Intervention Blocks

Introduction to ED Staff: Clinical Research Coordinators (CRCs) will set up their workstation in the ED and introduce themselves to ED staff (nurses, physicians and mid-levels), informing them that they will be doing the PROCOVAXED study that day.

They will avoid telling providers intervention vs non-intervention arms.

Initial Screening and Scripted Consent for Surveys: CRCs will review ED dashboards for inclusion and exclusion information. When an eligible patient is identified, the CRC will ask the nurse or doctor caring for the patient whether it is Ok for them to approach the patient about the first survey. Whenever possible, the CRC will ask the provider to first ask the patient if they may speak to them.

For provider approved patients: CRCs will approach eligible patients and deliver a scripted consent for two short surveys (Pre-intervention) FIRST SURVEY and the (Post-Intervention) SECOND SURVEY. See Scripted Consent for the Intervention periods.

Complete PROCOVAXED Screening. Enrollment log for all patients.

First Survey in the ED: For patients agreeing to the above surveys, we will administer a short survey – a baseline survey to be complete after obtaining scripted consent at the beginning of their ED visit (before exposure to the messaging platform intervention – PROCOVAXED FIRST SURVEY). CRCs will have the option of inputting survey responses to REDCap on iPads in real time or using paper surveys (and later inputting into REDCap). **These surveys are to be delivered orally (CRC asks questions), not via handing them out.**

Covid Vaccine Flyer, Videos and Telling Provider to Deliver Message: At the end of the survey, the CRC will deliver the Covid vaccine information flyer and ask the patient if they will watch a short video about Covid vaccines. If they agree to watch the video, the CRC will show them the video on the iPad. After finishing with the video, the CRC will tell the subject that they will be back in about an hour for the second survey. The CRC will then leave the room and tell the patient's primary provider (doctor, mid-level practitioner, or nurse) to deliver the message (hand them the scripted message).

Intervention: The intervention will consist of three messaging platforms to reduce vaccine hesitancy that have been produced in Specific Aims I and II:

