Second Survey (Post-Intervention) in the ED: We will administer a short survey approximately one hour after the intervention (after all 3 platforms). See SECOND SURVEY: INTERVENTION GROUP.

Complete Master Data Flow Log after each patient enrolled.

NOTE: All of the above study procedures should be performed in patient waiting times and not interfere or disrupt patient care in any way.

-

Study Procedures: Non-Intervention Blocks

The anticipated flow of the study during **Non-Intervention Blocks** is summarized in Figure 1.

Figure 2: Non-Intervention Blocks Study Flow

PROCOVAXED Trial Workflow on Non-Intervention Blocks

Introduction to ED Staff: Clinical Research Coordinators (CRCs) will set up their workstation in the ED and introduce themselves to ED staff (nurses, physicians and mid-levels), informing them that they will be doing the PROCOVAXED study that day.

CRCs will avoid telling providers intervention vs non-intervention arms.

Initial Screening and Scripted Consent for Surveys: CRCs will review ED dashboards for inclusion and exclusion information. When an eligible patient is identified, the CRC will ask the nurse or doctor caring for the patient whether it is Ok for them to approach the patient about the first survey. Whenever possible, the CRC will ask the provider to first ask the patient if they may speak to them.

For provider approved patients: CRCs will approach eligible patients and deliver a scripted consent for two short surveys: the Non-Intervention FIRST SURVEY and the Non-Intervention SECOND SURVEY. See Scripted Consent for the Non-Intervention periods.

CRCs will complete screening and enrollment log indicating whether or not they agreed to this survey. If they agreed to survey, CRC will assign a Study ID# and proceed to Master Data Flow form.

First Survey in the ED: For patients agreeing to the above surveys, we will administer a short survey – a baseline survey to be complete after obtaining scripted consent at the beginning of their ED visit (before exposure to the messaging platform intervention – PROCOVAXED FIRST SURVEY). CRCs will have the option of inputting surveys to REDCap on iPads in real time or using paper surveys (and later inputting into REDCap).

These surveys are to be delivered orally (CRC asks questions), not via handing them out. First Surveys are the same for intervention and non-intervention blocks.

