Second Survey in the ED: We will administer a second short survey at some time (approximately 1 hour) after the FIRST SURVEY. See SECOND SURVEY: NON-INTERVENTION GROUP. These second surveys in the non-intervention group have the same key primary and secondary outcome questions as in the INTERVENTION GROUP second surveys. SECOND SURVEY: NON-INTERVENTION GROUP.

NOTE: All of the above study procedures should be performed in patient waiting times and not interfere or disrupt patient care in any way.

- **Research Staff Informing of ED Providers when Participants will accept Covid vaccine**

At this time all of our EDs have the capability of administering COVID19 vaccines in some manner, and we expect that this will continue for at least the first 6 months of the trial. The last question in the SECOND SURVEY **in both arms** of the study is “Would you accept the Covid vaccine in the emergency department today if your doctor asked

you?" When a participant says they will accept the vaccine, the CRC or research staff will ask the patient if they can notify the patient's providers (nurse and/or physician) that they said they will accept the vaccine. They will also ask the patient if they (the CRC) can check to see if the patient receives the vaccine in the ED.

Other than this question and notification, research staff will not push that they get vaccinated.

- **Consent for 1- Month Follow Up Surveys for patients saying No to Vaccine in ED**

For all patients saying **no** to the question "*Would you accept the Covid vaccine in the emergency department today if your doctor asked you?*", research staff will ask if they can contact them and review their records in a month for follow up via full written consent. If patient says yes, then the CRC will get full **written** informed consent, including a separate HIPAA form, for review of their records and phone call. See FOLLOW UP Consent. Patients will not be compensated for participation. We will then ask Subjects for their best phone number(s) to reach them for a follow-up phone call. Sites will maintain a separate password protected database of subject IDs and follow up phone #s. Patients may agree to a phone call and not the EHR review, or vice versa. In those cases obtain the relevant consent, and note that they have accepted only one or the other.

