With this same baseline 15% rate of uptake and the same specifications for power, we will need to enroll 1,290 patients (645 in each arm) to detect a vaccine uptake difference (the primary outcome of Specific Aim IV) of 7%. Thus, our target enrollment for this implementation trial is 1290 subjects across all sites.

In terms of total projected time for enrollment, we expect a minimum enrollment of 1 subject per site per day (6 hour block) at the 5 sites, or 25 enrollees per 5 day work week. We therefore expect to attain our target enrollment of 1290 subjects in approximately 50 weeks.

- **Consents and Rationale**

Survey Consent We will obtain scripted verbal consent for the surveys in the usual manner that we have conducted other survey studies of similar design and scope - (CHR. See 2 versions of this Scripted consent for the Intervention periods and for the Non-intervention periods. (Intervention and Non-Intervention).

We will obtain written consent for follow up chart review and phone calls. See FOLLOW UP Consent.

With regards to consent for delivery of the intervention (Covid vaccine

messaging) during intervention periods, we must emphasize that messaging for vaccine hesitancy is firmly a part of standard best-practice emergency department care (messaging of this type is currently be enacted in EDs across the US). Delivery of all of the vaccine messaging platforms is therefore an accepted common best practice not requiring consent. To add an extra layer of consent could even lead to greater vaccine hesitancy. We therefore plan the following processes with verbal assent during the PROCOVAXED FIRST SURVEY in intervention months:

- Handing patients the Covid vaccine message information sheet at the end of the first survey.
- Informing the patient's provider(s) of the short scripted vaccine message to deliver to the patient sometime after the FIRST SURVEY
- At the end of the FIRST SURVEY, asking patients if they are willing to watch the vaccine messaging video(s). If the patient says Yes, then we will play the video. If the patient says no, we will not play the video.

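### Survey consent uses a different script in each arm, read after randomization and before baseline, so enrollment could depend on the arm; one common script would remove that route

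*Combined protocol and SAP*

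**What the plan says.** Section XIX (Consents and Rationale) obtains verbal consent to the surveys from a script in two forms: "See 2 versions of this Scripted consent for the Intervention periods and for the Non-intervention periods". The procedures follow this. Section IX (Intervention Blocks) says "See Scripted Consent for the Intervention periods", and Section X (Non-Intervention Blocks) says "See Scripted Consent for the Non-Intervention periods". In both sections the consent is for two short surveys.

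The script comes before any data collection. The First Survey is "a baseline survey to be complete after obtaining scripted consent at the beginning of their ED visit". By then the week's allocation is fixed under Section V (Randomization), and the coordinator who reads the script also runs that week's procedures.

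The content being consented to is largely common to the arms. Section X says "First Surveys are the same for intervention and non-intervention blocks". The second survey has a separate form for each arm, but "These second surveys in the non-intervention group have the same key primary and secondary outcome questions as in the INTERVENTION GROUP second surveys". Messaging is handled apart from survey consent: "Delivery of all of the vaccine messaging platforms is therefore an accepted common best practice not requiring consent". Section XIX asks about the video only once the First Survey is finished.

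The Primary Analysis (Section XVI) takes the patients surveyed as its population. Section XV (Data Recording and Entry) logs study arm and agreement to the first surveys for everyone approached.

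**The concern.** In a cluster trial that recruits patients after their cluster is allocated, the consent step decides who is compared. If the two scripts give a patient different impressions of what will follow, agreement can vary by arm. It can vary most with attitude to the vaccine, which is what the primary outcome measures.

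Patients who decline after hearing the script are not surveyed and leave the comparison. Intention to treat starts from those who agreed, so it cannot bring them back. The model in Section XVI has terms for arm, center and time and names no patient covariates. Adding covariates would be only a partial repair, because decliners have no survey data.

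The plan explains why messaging needs no consent, but not why consent to the surveys needs two wordings. The difference is part of the written procedure, so it can be removed without touching the intervention.

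**Working it through.** **Inputs from the documents.** Section XVIII gives a control rate of 15%, a target difference of 7 points (15% to 22%), alpha 0.05, power of at least 0.90, and 645 per arm (1,290 in total). It does not state sidedness.

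**Inputs that are assumed.** The documents give no consent rates. Let r be the agreement rate of hesitant patients (who would refuse the vaccine) divided by that of willing patients (who would accept it). Take r = 1 in control weeks and vary it in intervention weeks.

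**Step 1: reproduce the plan's figure.** For a two-sided pooled two-proportion test without continuity correction, the mean proportion is 0.185 and

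n = [1.960·√(2·0.185·0.815) + 1.282·√(0.15·0.85 + 0.22·0.78)]² / 0.07² = [1.076 + 0.701]² / 0.0049 ≈ 645 per arm, or 1,290 in total.

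This matches exactly, and power at 645 per arm is 90.0%. The point does not dispute this figure.

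**Step 2: effect of unequal agreement on the enrolled rate.** With no true effect, 15% of approached patients are willing in both arms. Among those enrolled in intervention weeks the proportion is

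p = 0.15 / (0.15 + 0.85·r).

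- r = 0.95: 0.15/0.9575 = 15.7%, difference +0.7 points
- r = 0.90: 0.15/0.915 = 16.4%, difference +1.4 points
- r = 0.80: 0.15/0.830 = 18.1%, difference +3.1 points

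**Step 3: probability of a significant result.** Let d = p − 0.15 and let m be the mean of p and 0.15. Then se0 = √(2m(1−m)/645) and se1 = √([p(1−p) + 0.15·0.85]/645). The upper-tail probability is 1 − Φ((1.960·se0 − d)/se1), to which the small lower tail is added.

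For r = 0.80: d = 0.0307, se0 = 0.0207 and se1 = 0.0207, so the argument is about 0.475 and the rejection rate is 31.8%. For r = 0.90 it is 10.6%, and for r = 0.95 it is 6.3%, against a nominal 5%.

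**Step 4: scale.** To produce the whole 7-point target with no effect, r would have to be 0.15·0.78/(0.22·0.85) = 0.63.

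**Step 5: the other direction.** Suppose the true intervention rate is 22% and hesitant patients agree 1/0.9 times as readily as willing ones in intervention weeks. The enrolled rate is 0.22/(0.22 + 0.78/0.9) = 0.22/1.0867 = 20.2%, and power falls from 90% to about 70%.

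Steps 3 and 5 use the individual-level variance of the plan's own sample-size formula, with no allowance for clustering.

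**The case against.** The strongest reply is that the scripts themselves are not in the available text. Bias needs wording that changes who agrees, and nothing visible shows such wording. The versions might differ only in title or in how they describe the second survey. Section XVI says receipt of messaging is ascertained by questioning patients in the outcome survey, so the intervention form may carry extra items. That would be an ordinary reason for two scripts. Section XIX also keeps assent to messaging out of the opening consent, so the scripts may already be neutral.

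This stands as a limit on what can be claimed. A reader might infer that the intervention script announces vaccine messaging and so drives hesitant patients away. The documents do not support that. The pre- and post-intervention labels in Section IX are staff-manual terms. Section X applies similar language to control weeks, where no intervention follows, so the labels do not show what patients hear. It would also be too strong to say that the two arms complete the same two surveys, since only the First Survey is stated to be identical.

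Two smaller replies are also fair. The primary model uses no First Survey covariate, so any effect of the script on baseline answers does not enter the primary estimate. The data needed to monitor agreement are already logged, although no comparison by arm is planned.

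None of this supplies a reason to keep two wordings. Coordinators avoid naming the arm to providers, but that does not change what the patient is told.

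**Conclusion.** The point holds as a removable weakness in the design, not as a demonstrated bias. Two arm-specific scripts stand between randomization and enrollment, the analysis is confined to those who agree, and the plan's own reasoning on consent gives no need for the difference.

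The illustrative range is +0.7 to +3.1 points, with rejection rates of about 6% to 32% when there is no effect. It rests on assumed relative agreement of 0.95 to 0.80, a 15% control rate, 645 per arm and individual-level variance. The same mechanism in reverse would hide a true effect. These figures show how sensitive the comparison is to unequal agreement. They do not show that the trial's result will be inflated, and a reader should not infer a direction from them.

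**What to change.** Replace the two scripts with one, worded identically in both arms up to the point of agreement and covering two short surveys about an hour apart. Amend Sections IX, X and XIX to cite that single script. Keep the request to watch the video at the end of the First Survey in intervention weeks, as Section XIX already provides. Add to Section XVI a report, by arm, of the numbers approached and the numbers agreeing, taken from the enrollment log described in Section XV.

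The cost is a minor IRB amendment. Any mention of messaging now in the intervention script would move to the later assent step. The sample size is unchanged and no new data are needed.

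The change does not remove selection by coordinators, who know the week's arm when they approach patients. Reporting agreement by arm would help show whether that, or any remaining difference, is affecting who enters.
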